Qualitative Interviews. At the end of their participation in CBT-I, participants in Part 2 will complete a qualitative interview that will take approximately 60 minutes regarding their sleep experiences and feedback about CBT-I materials and guidelines. The qualitative interview will be audiorecorded. Audiorecordings will be transcribed by an experienced VA-approved transcriptionist. The transcriptionist will not know the identities of the participants on the recordings and recordings will not include any identifying information. Research staff will ensure that the audiorecordings are transferred in a secure manner (encrypted) to the transcriptionist. Participants will be paid \$40 for completion of the qualitative interview.

Time Point 2 Assessment Battery. At the end of their participation in CBT-I, participants in Part 2 will also complete the ISI and the assessment battery administered in Part 1 Time Point 1 Assessment Battery. Participants will be paid \$30 for participation in this assessment battery.

Phase 2 (RCT) has two parts:

Part 1: Consent and Time Point 1 Assessments (n=190) and

Part 2: Treatment with CBT-I or Health and Wellness, Time Point 2 Assessment Battery, and Time Point 3 (Follow Up) Assessment Battery (n=60; invited from the 190 in Part 1), Qualitative Interview (n=30)

Part 1: Consent and Time Point 1 Assessments. Part 1 will follow the same assessment procedures as Phase 1, Time Point 1 with the exception that all participants who complete the ISI and score 15 or higher will receive a WatchPAT device. If participants are unable to obtain a valid reading on the WatchPAT device but they have had a

HP-00074686 4/19/22, 11:30 AM

VA sleep apnea screening study in the past 6 months that generated an apnea hypopnea index (AHI) score, this number will be used in place of the unattainable WatchPAT reading. Participants who complete the ISI and score lower than 15 will not be eligible to continue in the study and will be paid \$5 for their participation. Participants who complete the Time Point 1 Assessment Battery will be paid \$30. Each participant will be paid \$75 when they participate in the home sleep apnea

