Part 2: Treatment with CBT-I or Health and Wellness. Participants will be recruited for Part 2 until 60 participants are screened eligible and have agreed to participate. We anticipate screening 190 records and participants in order to recruit 60 participants for Part 2. Participants will be randomized to either the CBT-I (treatment) condition or the Health and Wellness (control) condition. Procedures for Part 2, Treatment are otherwise the same as in Phase 1, Treatment, with the exception that we will not pose open-ended questions to participants about recommendations for changes to the treatment.

Time Point 2 Assessment Battery. The Time Point 2 Assessment Battery will follow the same assessment procedures as in Phase 1. Approximately two weeks prior to the Time Point 2 (Post) Assessment date, participants may be given an Actiwatch and will be given sleep diaries to complete. Participants will be paid \$30 for participation in the post quantitative assessment battery. If a Veteran is unable to complete the study assessment at a VAMC and does not wish to complete the full assessment battery via telephone, then we will offer to conduct the 7-item Insomnia Severity Index (ISI) measure over the phone and strongly encourage the Veteran to choose a confidential location for this questionnaire.

Time Point 3 (Follow up) Assessment Battery. At 3 months following the intervention, participants will complete the Time Point 3 (Follow Up) Assessment Battery used in Time Points 1 and 2. Approximately two weeks prior to the Time Point 3 (Follow Up) Assessment date, participants may be given an Actiwatch and will be given sleep diaries to complete. Participants will be paid \$30 for participation in the follow up quantitative assessment battery. If a Veteran is unable to complete the study assessment at a VAMC and does not wish to complete the full assessment battery via telephone, then we will offer to conduct the 7-item Insomnia Severity Index (ISI) measure over the phone and strongly encourage the Veteran to choose a confidential location for this questionnaire.

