Phase 2 (RCT): Specific Aim 3, Hypothesis 1 (H1). CBT-I intervention feasibility will be demonstrated by adequate rates of recruitment, initial intervention engagement, attendance at intervention sessions, and therapist fidelity. Analysis: We will use descriptive statistics to summarize the feasibility of CBT-I by: Calculating (a) the rate of recruitment (# consented divided by # approached and # randomized divided by # consented) and compare these to recruitment goals; (b) the percent who engaged in treatment (% of randomized who attend first 3 sessions), median (and inter-quartile range [IQR]) of the total number of sessions attended and treatment dropout rates (# who dropped out prior to completing treatment divided by # who engaged); (c) the median (and IQR) of the number of reminders and outreach contacts made for each participant; (d) the mean (and SD) of the CBT-I Treatment Components Adherence Scale assessed at post-treatment; and (e) the percent of participants who turned in completed sleep logs and percent of the total number of treatment sessions in which completed sleep logs were turned in. To assess therapist fidelity to CBT-I, we will compute percent of sampled sessions in which interventionists were adequately adherent as defined by the rollout criteria of the VA CBT-I EBP of an average rating equal to 2 ("satisfactory"), in addition to no items at a score of 0 ("poor") on the Assessment Competency Rating Scale and the Therapy Competency Rating Scale. For the Health and Wellness condition, we will also compute percentages of sampled sessions with adequate adherence on our Health and Wellness Therapist Adherence and Competence rating scales with parallel criteria for adequacy (i.e. average score equal to "acceptable" and no items scored as "unacceptable").

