- * Describe anticipated circumstances under which subjects will be withdrawn from the research without their agreement: Veteran Participants will be withdrawn without their agreement under the following circumstances:
 - 1) They have a serious reaction during the study
 - 2) They fail to follow instructions from research staff
 - 3) If the PI decides that the study is no longer in the best interest of the participant.

These circumstances have been outlined in the VA mandated informed consent form.

* Describe procedures for orderly termination:

We will close the study after the last participant interaction occurs and all data has been collected.

* Describe procedures that will be followed when subjects withdraw from the research, including partial withdrawal from procedures with continued data collection:

If a participant decide to withdraw from the research, all data already collected will remain in the database, but no new data will be collected from the participant. This information is included in the VA mandated consent form.

ID: VIEW4E1B52531F800 Name: v2_Withdrawal of Participants

HP-00074686 Privacy of Participants V2

Privacy of Participants

If the study does not involve interaction with participants, answer "N/A" to the questions below.

* Describe how you will ensure the privacy of potential participants throughout the study (privacy refers to persons and their interest in controlling access to themselves):

Research staff are thoroughly trained to protect the privacy of research participants. We meet with participants in private rooms with closed doors at the VAMHCS.

* Describe the location where potential participants will receive research information and detail the specific actions the study 2 team will take to ensure adequate privacy areas: Participants will receive research information in a private room with the door closed within the VA Maryland Health Care System (VAMHCS).

3	* Describe potential	environmental	stressors	that may	be associa	ated with	the	research
	There are no environment	al stressors associa	ated with this	research				

4	* Will this study have a site based in the European Union?
	Yes No

5	* Will the study have planned recruitment or data collection from participants while they are located in the European Union?
	Yes No

Access link below for information about the EU General Data Protection Regulations to assist in answering these questions. https://www.umaryland.edu/oac/general-data-protection-regulation/

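### Withdrawing randomized participants for not following staff instructions, with no route to keep assessing them, can lose outcomes for a reason tied to adherence

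*Combined protocol and SAP*

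**What the plan says.** Withdrawal of Participants, first item, gives three grounds on which staff will remove a participant from the research without that person's agreement. The second is "They fail to follow instructions from research staff". No threshold or definition is attached. The other two are a serious reaction and the PI's judgement of the participant's best interest.

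The third item of that section asks what happens on withdrawal, "including partial withdrawal from procedures with continued data collection". The answer addresses only a participant who decides to leave: "all data already collected will remain in the database, but no new data will be collected from the participant".

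The outcome visits are in Study Procedures:

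- Time Point 2, Phase 1: "At the end of their participation in CBT-I, participants in Part 2 will also complete the ISI and the assessment battery".
- Time Point 2, RCT: "The Time Point 2 Assessment Battery will follow the same assessment procedures as in Phase 1".
- Time Point 3, RCT: "At 3 months following the intervention, participants will complete the Time Point 3 (Follow Up) Assessment Battery".
- Fallback at both RCT visits, if the Veteran cannot attend and does not want the full battery by telephone: "then we will offer to conduct the 7-item Insomnia Severity Index (ISI) measure over the phone".

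Treatment is about 10 sessions over about 4 months, and the number of sessions varies with how quickly insomnia improves.

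The feasibility analysis (Specific Aim 3, Hypothesis 1) summarizes sessions attended, treatment dropout, an adherence scale at post-treatment and "the percent of participants who turned in completed sleep logs".

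**The concern.** Not following instructions is a post-randomization event, and it may be related to how the participant is sleeping or responding. A rule that removes such people from the research, and not only from sessions, can turn non-adherence into missing outcomes. The remaining participants in each arm are then no longer exactly the randomized groups. The form's own prompt invited a partial-withdrawal route, and the answer does not provide one.

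The rule also conflicts with the plan's feasibility aim. Summaries of attendance, returned sleep logs and adherence at post-treatment are informative only if poorly adherent participants stay in the study. A reader cannot tell which of the two the team will do.

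**Working it through.** **1. The passages side by side**

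| What happens to a randomized participant | Time Point 2 | Time Point 3 |
|---|---|---|
| Finishes sessions | At the end of participation in treatment | 3 months later |
| Stops sessions early, stays in the research | Can be read as covered, but not stated; the wording names only CBT-I | Date not defined |
| Chooses to leave the research | No new data | No new data |
| Removed by staff for not following instructions | Not stated | Not stated |

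An illustration of the undefined date: suppose someone stops after 1 month (assumed). Three months after the last session is month 1 + 3 = 4. Three months after the planned end of treatment is month 4 + 3 = 7. The text supports either.

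**2. The plan's own figures reproduce**

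Inputs from Sample Size and Data Analysis: 30 per arm, 25% loss at post-treatment, 35% at follow-up, d = 0.60, r = 0.7. No alpha is stated; 0.05 two-sided is assumed.

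- Retained: 30 × 0.75 = 22.5 and 30 × 0.65 = 19.5 per arm, matching the stated 22-23 and 19-20.
- Power ≈ Φ(d/√(1−r²) × √(n/2) − 1.96). Here 0.60/√0.51 = 0.840; 0.840 × √(22.5/2) = 2.818; 2.818 − 1.96 = 0.858; Φ(0.858) = 0.805.
- The noncentral t with 2n−3 degrees of freedom gives 0.786 at 22.5 and 0.795 at 23 per arm.
- With d = 0.67 and r = 0.6, the figures at 22.5 are 0.802 (normal) and 0.784 (t).

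The stated 0.80 stands within about 2 points.

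**3. How large could the bias be?**

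The documents give no rate of staff withdrawal, so a simulation needs assumptions:

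- 30 per arm, unit SD, no true effect, baseline to post-treatment r = 0.7 (from the plan).
- Session ISI correlates 0.8 with post-treatment ISI and 0.65 with baseline (assumed).
- Total loss is 25% per arm. In the CBT-I arm, 1, 2 or 3 of 30 (3% to 10%) are lost with a logistic dependence on session ISI; all other loss is random.
- Complete-case baseline-adjusted ANCOVA at post-treatment; 6,000 replicates; Monte Carlo SE about 0.003 SD.

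Bias toward CBT-I in SD units, when poor responders leave:

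| Lost informatively | slope 0.5 per SD | slope 1.0 | slope 1.5 |
|---|---|---|---|
| 1 of 30 | 0.011 | 0.015 | 0.016 |
| 2 of 30 | 0.011 | 0.021 | 0.032 |
| 3 of 30 | 0.017 | 0.032 | 0.047 |

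- Type I error is 4.8% to 5.8%.
- If improvers leave instead, the bias is 0.008 to 0.043 SD against CBT-I, with type I error 5.0% to 5.7%.
- If the same mechanism acts in both arms, it is below 0.005 SD.

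For scale, the SE of the estimate is √(2 × 0.51/22.5) = 0.213 by formula and about 0.22 in simulation. The largest bias above is 0.047/0.22 ≈ 0.21 of a standard error. The documents give no SD for the ISI, so this cannot be converted to ISI points.

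**4. What continued assessment buys**

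Regaining half of the informative losses by telephone cuts the bias to 0.001-0.014 SD. If loss depends on the unseen final ISI instead of session ISI, the range falls from 0.006-0.060 to 0.002-0.021 SD.

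**The case against.** The strongest reply is that little is at stake. This is a small feasibility and preliminary-efficacy trial, the bias is a fraction of a standard error, and its sign cannot be predicted. The risk section describes possible discomfort in both arms, so the plan gives no reason to expect different loss by arm. All of this stands and limits the weight of the point.

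Second, the Time Point 2 wording is tied to the end of a participant's own participation, and the number of sessions varies. It can fairly be read to include early stoppers. The feasibility analysis also treats treatment dropout separately from loss to follow-up, which suggests that non-adherent participants are usually kept. A reader might infer that early stoppers are never assessed; the documents do not support that. They leave it unsaid, and they leave unsettled the Time Point 3 date and everything after a staff withdrawal.

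Third, a reader might take the no-new-data sentence to cover staff withdrawals too. It is worded only for people who choose to leave. If it were meant more widely, the loss of outcomes would be certain where it is now only possible.

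Fourth, the consent form that the section refers to is not in the review copy, and the Hypotheses 2a-b text relies on a mixed model described earlier that is not there either. Either source may say more. For that reason the absence of a named analysis set is not pressed here as a defect in its own right.

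Finally, the form was printed in April 2022 and describes COVID-era payments in the past tense, so some outcome visits have probably passed. That reduces the benefit of a change but does not remove the ambiguity in the text.

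**Conclusion.** The point holds in a limited form. The rule as written removes randomized participants from the research for non-adherence, offers no way to keep assessing them, does not say whether outcomes are sought afterwards, and leaves Time Point 3 undated for early stoppers. It needs to be reconciled with the adherence summaries in the same plan.

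The likely bias is about 0.01-0.05 SD if 1-3 of 30 CBT-I participants are lost informatively, in either direction, and about zero if the arms behave alike. This rests on assumed loss mechanisms, assumed session-ISI correlations and an assumed number of such withdrawals.

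Three stronger conclusions are tempting and unsupported:

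- That the result is biased in favour of CBT-I: the sign depends on who leaves, which the plan does not show.
- That the bias could reach about 0.10 SD: this requires all 25% of CBT-I loss to depend on insomnia while all control loss is random, which goes far beyond the withdrawal rule.
- That the trial is underpowered: the stated power reproduces.

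The case for acting is that the procedure is undefined and inexpensive to define.

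**What to change.** - In Withdrawal of Participants, separate stopping sessions from leaving the research, so that not following instructions or stopping sessions does not by itself end outcome assessment. Whether and when sessions stop remains the investigator's decision.
- In both arms, seek Time Points 2 and 3 from these participants if they still consent, at minimum the telephone ISI already provided for. Aim for about when the visits would have been due had sessions continued, using the plan's own intervals of about 4 months and then 3 months.
- State that all randomized participants are analysed by assigned arm in the Hypotheses 2a-b model.
- Reconcile the withdrawal rule with the attendance, sleep-log and adherence summaries under Hypothesis 1.
- Leave the serious-reaction and PI best-interest grounds, and the continued-consent provision in Informed Consent Process, as written.

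Cost: protocol and consent wording and a few short calls, with no new instrument. Visit timing will vary somewhat, because early stoppers would follow the planned calendar while others are timed from the end of treatment. The telephone ISI alone does not supply the VR-36, and participants already past these visits gain little. A supportive analysis using session ISI, or a not-missing-at-random sensitivity analysis, is optional and not part of this point.

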1.2.2 Name Created **Modified Date**

Compensation for Research Related Injury(0.02)

4/5/2017 5:33 PM

ID: VIEW4E1B629EEC000
Name: v2_Compensation for Research-Related Injury

4/19/2017 11:17 AM

HP-00074686

Payment to Participants_V2

HP-00074686

Payment/Reimbursement to Participants

* Will participants receive payment (money, gift certificates, coupons, etc.) or reimbursement for their participation in this research?

Yes No

ID: VIEW4E1C52A5D7800 Name: v2_Payment to Participants

HP-00074686 4/19/22, 11:30 AM

HP-00074686 Payment Detail V2

Payment/Reimbursement Detail

You indicated that participants will receive payment (money, gift certificates, coupons, etc.) or reimbursement for their participation in this research.

ent/reimbursement to participants will be for: (check all that apply) avel arking eals adging me and effort ther er, specify: is the total dollar value of the payments/reimbursements over the duration of the study? Total payment(s) for participation
eals adding me and effort ther er, specify: is the total dollar value of the payments/reimbursements over the duration of the study? Total payment(s) for participation
is the total dollar value of the payments/reimbursements over the duration of the study? Total payment(s) for participation
me and effort ther er, specify: is the total dollar value of the payments/reimbursements over the duration of the study? Total payment(s) for participation
her er, specify: is the total dollar value of the payments/reimbursements over the duration of the study? Total payment(s) for participation
er, specify: is the total dollar value of the payments/reimbursements over the duration of the study? Total payment(s) for participation
is the total dollar value of the payments/reimbursements over the duration of the study? Total payment(s) for participation
arch of \$600 or more in a calendar year is required to be reported on an IRS Form 1099. D5
ribe the timing and distribution plan for the payment/reimbursement (schedule, means, etc.)? cipant expresses to study staff they he or she is having difficulty attending study appointments due to lack of transportation then a bus token, or equivalent trave will be offered to the participant.
(Acceptability Trial)
onsent and Time Point 1 Assessments: ipants at \$5 each for demographic and ISI form (if deemed ineligible due to ISI score); \$30 each for Time Point 1 Assessment Battery and \$75 each for sleep creening, depending on meeting eligibility criteria.
ualitative Interviews: pants at \$40 each for qualitative interviews.
me Point 2 Assessment Battery: oants at \$30 each for Time Point 2 Assessment Battery.
(RCT)
onsent and Time Point 1 Assessments: cipants at \$5 each for demographic and ISI form (if deemed ineligible due to ISI score); \$30 each for Time Point 1 assessment battery, and \$75 each for sleep creening, depending on meeting eligibility criteria.
me Point 2 Assessment Battery: ipants at \$30 each for Time Point 2 Assessment Battery.
me Point 3 (3-month Follow-Up) Assessment Battery: ipants at \$30 each for Time Point 3 Assessment Battery.
ualitative Interview: ipants at \$40 each for RCT Qualitative Interview.
od(s) of payment/reimbursement to be Used:
ash
neck Oney Order
ift Certificate/Gift Card
ther

If completing in person they will be given a VA voucher that they can take to the VA agent cashier and redeem for cash, or be sent a check from the VA Cashier or electronic gift card. A check from the VA Cashier or electronic gift card will be sent to Veterans if they are completing study procedures over the phone. Participants will be given bus tokens or equivalent travel voucher as needed.

If participants did not complete the MATRICS in-person due to safety issues surrounding COVID, they only received \$20 instead of \$30 for completion of the assessment over the phone.

ID: VIEW4E1C54A6ACC00 Name: v2_Payment Detail

HP-00074686 HIPAA_V2

HIPAA (Health Insurance Portability and Accountability Act)

* Are you affiliated with, or will you be accessing data from a HIPAA-covered entity? A covered entity might be a hospital, a physician practice, or any other provider who transmits health information in electronic form.

- At UMB, this includes UMB schools designated as covered entities (School of Medicine and School of Dentistry) and entities under the University of Maryland Medical System (UMMS). The Baltimore VA Medical Center is also a covered entity.
- If you are a researcher from any school that is not a covered entity but is accessing electronic medical records from a covered entity (such as UMMC), HIPAA would be applicable. Please see a list of covered entities included under UMMS here: executed-ace-designation-042018.pdf

Yes	\bigcirc	No
-----	------------	----

ID: VIEW4E1B0A2114400

Informed Consent Process

If the study does not involve interaction with participants or a waiver of consent is being requested, answer "N/A" to the questions below.

ill that apply)

* Describe the Informed Consent process in detail:

Our research staff are carefully trained on obtaining consent from participants with mental illness and supervised by senior staff members. If a potential participant indicates interest in participating, the study interviewer will meet the participant, introduce him/herself to the participant, provide an overview of the project, and invite him/her to participate. Interested participants are provided an informed consent form. Staff members are trained to recognize symptoms of severe mental illness and cognitive impairment that could undermine a participant's ability to provide informed consent. The consent form is reviewed in detail with all participants. Research staff are trained in strategies for interacting with people with severe and persistent mental illness, including speaking slowly and clearly, stopping to summarize frequently, and providing time for questions.

After the consent form has been summarized and reviewed and all questions answered, the staff confirms that the participant is still interested in participating by soliciting a verbal response. Those who express willingness to provide consent must complete a brief questionnaire to assess competency and understanding of the consent form (see evaluation to sign consent questions in additional documents). If the participant is unable to answer the questions correctly, staff re-reviews the aspects of the study that the participant did not understand. The staff member asks the questions a second time. If the participant cannot answer all questions correctly, he/she will not be enrolled in the study.

Per IRB regulations, a copy of the signed consent form is given to the participant, and the original is kept in the research office. Participants will also receive a Health Insurance Portability and Accountability Act Authorization to Obtain, Use and Disclose Protected Health Information for Research (HIPPA) that will be reviewed and summarized for them. Staff will ask participants if they have any questions once the document has been read, and then participants will sign the authorization. A copy of this signed form will be given to the participant, and the original is kept in the research office.

In keeping with the requirements put forth in the Department of Veterans Affairs: a) social security numbers of veterans will not be solicited; b) research staff will restrict telephone and other contacts with veterans to the procedures and data elements outlined in the IRB approved protocol; c) initial contact with veterans must be made in person or by letter prior to telephone contact and initial contact with veterans must be made in person or by phone prior to email contact; d) verification of the study will be provided following the guidelines set forth in HRPP/IRB policies and procedures 10G.

Request to Waive Documentation of Consent:

A waiver of documentation of consent is being requested because a participant developed some skin irritation under the wristband of one of the watches used in the protocol. For this new risk, we will request verbal consent by informing current participants of the risk as soon as possible, either via telephone or an in-person appointment, whichever would occur first, so they do not have to wait until their next study appointment to receive the information. Since this is believed to be a minimal risk, we wanted to minimize the burden that would be placed on participants to complete a written reconsent process. We also believe that this new information will not change participants' willingness to continue participation, as we will not ask them to continue wearing the watch should this situation arise. Study staff will use the script provided in "additional documents" and document this in participants' study records. If other anticipated risks would occur, this process will be evaluated on a case-by-case basis.

A waiver of written documentation of consent is being requested to inform participants of the option to complete assessments, the interview, and intervention sessions via telephone if needed, as well as to be emailed resources, materials, and/or response cards. We will request verbal consent by informing current participants as soon as possible, either via telephone or an in-person appointment, whichever would occur first, so they do not have to wait until their next study appointment to receive the information. Since this is believed to be minimal risk, we wanted to minimize the burden that would be placed on participants to complete a written reconsent process. We also believe that this new information will not change participants' willingness to continue participation, as we are broadening their options for remote participation. Study staff will use the script provided in "additional documents" and document this in participants' study records.

- * Confirm that the consent process will explain the following:
 - The activities involve research.
 - The procedures to be performed.
 - That participation is voluntary.
 - The name and contact information for the investigator.
 - Yes () No
- * Describe who will obtain Informed Consent:

The research staff listed in this protocol.

* If obtaining consent from a legally authorized representative (LAR), describe how you will confirm that the individual is the LAR and can provide legally effective informed consent. (Answer "N/A" if not obtaining consent from LARs) N/A

* Describe the setting for consent:

A private office or room with a closed door within the VAMHCS.

* Describe the provisions for assessing participant understanding:

Participants must correctly answer a set of questions regarding the study. If they do not answer all of the questions correctly after 2 attempts, they will not be eligible to participate.

* Describe the consideration for ongoing consent:
Staff will review the procedures of the protocol, potential risks and benefits, right to withdraw and how confidentiality of research data will be maintained with the participant before each interview. If they are not able to provide continued consent, they will be removed from the study.

ID: VIEW4E1C661D0AC00 Name: v2_Informed Consent Process

HP-00074686

Waiver of Documentation of Consent V2

Waiver of Documentation of Consent

You indicated that a waiver of documentation of consent (verbal/oral consent) is requested.

- * Indicate why a waiver of documentation of consent is being requested for the study:
 - The only record linking the subject and the research would be the consent document, and the principal risk would be potential harm resulting from a breach of
 - The research presents no more than minimal risk of harm to subjects, and involves no procedures for which written consent is normally required outside of the research context.

* Provide a justification/explanation for the choice above:

A waiver of documentation of consent is being requested because a participant developed some skin irritation under the wristband of one of the watches used in the protocol. For this new risk, we will request verbal consent by informing current participants of the risk as soon as possible, either via telephone or an in-person, whichever would occur first, so they do not have to wait until their next study appointment to receive the information. Since this is believed to be a minimal risk, we wanted to minimize the burden that would be placed on participants to complete a written reconsent process. We also believe that this new information will not change participants' willingness to continue participation, as we will not ask them to continue wearing the watch should this situation arise. Study staff will use the script provided in "additional documents" and document this in participants' study records. If other anticipated risks would occur, this process will be evaluated on a case-by-case basis.

A waiver of written documentation of consent is being requested to inform participants of the option to complete self-report assessments, the interview, and intervention sessions via telephone if needed, as well as to be emailed resources, materials, and/or response cards. We will request verbal consent by informing current participants as soon as possible, either via telephone or an in-person appointment, whichever would occur first, so they do not have to wait until their next study appointment to receive the information. Since this is believed to be minimal risk, we wanted to minimize the burden that would be placed on participants to complete a written reconsent process. We also believe that this new information will not change participants' willingness to continue participation, as we are broadening their options for remote participation. Study staff will use the script provided in "additional documents" and document this in participants' study records.

> ID: VIEW4E1C6EF6F5000 Name: v2_Waiver of D

HP-00074686

Waiver - Alteration of Consent V2

Waiver or Alteration Consent Process

You indicated that a waiver/alteration of consent is requested.

- * Explain why the research involves no more than minimal risks to the subjects: This request for waiver of informed consent is for recruitment purposes only, as required by the VA for studies that also obtain a waiver of HIPAA authorization for recruitment purposes. We will view information to determine eligibility but no research procedures will be conducted until such time that the participant agrees to take part in the study and signs the informed consent document. The recruitment process involves no more than minimal risk to the individual.
- * Explain why a waiver or alteration of the consent process would not adversely affect the rights and welfare of the subjects: This waiver request is for recruitment purposes only as required by the VA. If it is determined that the individual would be eliqible to take part in the study, they will be approached and given the opportunity to agree and sign the informed consent document or they can decline participation.
- * Informed consent is always required unless there is reason to grant a waiver or alteration of the consent process. Explain 3 why you cannot carry out the research unless you are granted a waiver or alteration of the consent process: This waiver request is for recruitment purposes only as required by the VA. If it is determined that the individual would be eligible to take part in the study, they will be approached and given the opportunity to agree and sign the informed consent document or they can decline participation.
- If the research involves using identifiable private information or identifiable biospecimens, please explain why the research could not practicably be carried out without using such information or biospecimens in an identifiable format.
- In some cases there will be additional pertinent information during the study that should be given to the participating subjects. For those subjects who have not been given informed consent because there is a waiver or alteration of the consent process, explain how the subjects will receive this additional important information. If applicable, please explain why a subject would not receive additional pertinent information. N/A. Individuals who would be eligible to take part in the study will be given the opportunity to agree and sign the informed consent document or to decline participation.
- If you are requesting an alteration of the consent process please explain why this request is necessary for the conduct of the research study. Please identify specifically what is being altered or changed in the consent process.

ID: VIEW4F1C73B344800 Name: v2 Waiver/Altera

Consent and HIPAA Authorization Forms - Draft

Upload all of your Consent Forms for approval. Use only Microsoft Word.

Name	Created	Modified Date
VAMHCSConsent_Acceptability_CBT-I_8-16-19 clean.docx(0.02)	8/16/2019 1:02 PM	8/16/2019 2:29 PM
© CBT-I RCT ICF 3-24-20 track changes.docx(0.03)	3/16/2020 4:52 PM	3/24/2020 12:32 PM
VAMHCSConsent_Acceptability_CBT-I_8-16-19 track changes.docx(0.02)	8/16/2019 1:02 PM	8/16/2019 2:29 PM
CBT-I RCT ICF 3-24-20 clean version_updated(0.01)	12/2/2020 10:31 AM	12/2/2020 10:31 AM

IMPORTANT NOTE: the above list of consent forms (if any) are DRAFT versions. Under no circumstances should copies of these be distributed to patients/study subjects. If/when this research submission is approved by the IRB, approved consent forms will be available for download and use from the "Documents" tab of the Submission's workspace (click Exit and then look for the Documents tab - approved submissions only)

Archived Consent Forms:

Name	Created	Modified Date	
☐ CBT-I RCT ICF 3-24-20 clean.docx(0.03)	3/16/2020 4:52 PM	3/24/2020 12:32 PM	
CBT-I RCT ICF 8-28-19 track changes.docx(0.03)	8/16/2019 12:55 PM	8/28/2019 11:29 AM	
CBT-I RCT ICF 8-28-19 clean.docx(0.03)	8/16/2019 12:56 PM	8/28/2019 11:29 AM	
CBT-I RCT ICF 8-14-19 clean.docx(0.01)	8/16/2019 12:55 PM	8/16/2019 12:55 PM	
VAMHCSConsent_RCT_CBT-I _5.09.18_clean.docx(0.05)	9/13/2017 9:36 AM	1/7/2019 2:38 PM	
VAMHCSConsent_RCT_CBT-I _5.09.18 tracked changes.docx(0.05)	3/30/2018 10:47 AM	1/7/2019 2:37 PM	
VAMHCSConsent_Acceptability_CBT-I_9.12.17.docx(0.03)	9/13/2017 9:36 AM	10/23/2017 3:25 PM	

Upload any HIPAA authorization forms here:

Acceptability HIPAA.pdf(0.01)	8/23/2017 10:31 AM	8/23/2017 10:31 AM
RCT HIPAA.pdf(0.01)	8/23/2017 10:31 AM	8/23/2017 10:31 AM

Please refer to HRPO's website for specific instructions for preparing informed consent documents and to access current templates: http://hrpo.umaryland.edu/researchers/consents.html

ID: VIEW4E1C7712D3000 Name: v2 Consent Forms - Draft

Organization Review Requirements (other than IRB)

Answer the following questions to determine additional organizational review requirements:

Department / Division Review - All research submissions are required to undergo department/division/institutional review

•	prior to IRB review. The following entity is listed as the required department/division/institutional review:	Silai review
	Psychiatry	
	If this information is incorrect, please notify the HRPO office.	
2	RSC Review Criteria - select 'Yes' if the answer is 'Yes' for any of the following questions. Review by the Radiat Committee may be required.	ion Safety
	* 2.1 Does the research involve the use of ionizing radiation?	Yes No
	2.2 Does the research involve the sampling of radioactive human materials for subsequent use or analysis in a laboratory?	
3	IBC Review Criteria - select 'Yes' if the answer is 'Yes' for any of the following questions. Review by the Institut Biosafety Committee may be required.	ional
	* 3.1 Does the research involve human gene transfer? -OR-	Yes No
	Does the research specifically apply to human studies in which induction or enhancement of an immune response to a vector-encoded microbial immunogen is the major goal, and such an immune response has been demonstrated in model systems, and the persistence of the vector-encoded immunogen is not expected? This type of research is often referred to as recombinant vaccine trials.	
	3.2 Does the research involve the exposure of human subjects to pathogenic microorganisms, or the exposure of research staff to human subjects or samples known or reasonably expected to carry infectious disease(s)?	
	3.3 Does the research involve the sampling of materials from persons with no known infectious disease and where the only risk to study staff is occupational exposure to bloodborne pathogens as defined by the OSHA Bloodborne Pathogen Standard?	
4	Cancer Center Criteria - Answer the following to determine if review by the Cancer Center (Hematology-Oncolo	ogy) may
